12.2.4. Electrocardiogram

Standard 12-lead ECGs will be collected at the Screening visit 1 and at EOT/EOS. The Investigator or designee will review the 12-lead ECG and findings will be recorded in the CRF as normal, abnormal but not clinically significant, or abnormal and clinically significant. Any clinically significant abnormality on ECGs should be reported on the AE CRF page.

Investigative sites must retain a copy of all 12-lead ECGs evaluated by the Investigator or designee. These ECGs must be clearly labeled with the subject's initials, Subject ID number, date, and time.

12.2.5. Dual Emission X-Ray Absorptiometry

A bone density assessment will be done using the DEXA scan.

12.2.6. Subject Questionnaires

Information about the subject's PBC disease history (ie, date of diagnosis, treatment history, pruritus history, signs and symptoms, and including smoking history) will be collected during Screening. At subsequent study visits (see [Section 7.1.2](#)), subjects will be asked to complete the following questionnaires; they may be asked to initial and date to document confirmation of their responses, and the questionnaires should be filed in the subject's study records. These may require transcription to the CRF by study site staff.

- 5-D Pruritus Questionnaire: This is a questionnaire that has been validated in several different diseases. It assesses symptoms in terms of 5 domains: degree, duration, direction, disability and distribution (Elman 2010).
- Pruritus VAS: A Visual Analogue Scale (VAS) will also be used to assess pruritus in individual subjects.

12.2.7. Laboratory Assessments

Subjects will be instructed to attend each of their study visits (except Screening) in a fasted state, and subjects should remain fasted until their blood samples have been collected. At each visit, the Investigator or designee will verify that the subject has fasted for at least 8 hours and record fasting status in the source and CRF. If the subject reports having eaten (water is permitted) within 8 hours, the Investigator or designee will document accordingly in the source and CRF and remind the subject that fasting is required prior to all study visits.

Blood samples for serum chemistry and hematology will be collected at every visit as detailed in the Schedule of Study Procedures (Section 7.1.2). The number and volume of samples to be collected at each visit will be detailed in the laboratory manual.

Full instructions concerning the number and type of samples to be collected at each visit, the required sample volumes, sample collection methods, sample processing, labeling, and shipping will be provided by the central clinical laboratory in a study specific laboratory manual. All necessary collection supplies will be provided by the central laboratory and will be appropriately assembled for the specific evaluations required at each visit.

All subjects with laboratory tests containing clinically significant abnormal values are to be followed regularly until the values return to normal ranges; until a valid reason, other than investigational product-related AE, is identified; or until further follow up is deemed medically unnecessary.

Laboratory samples will be stored for a maximum of up to 1 year after the end of the study (depending on stability) in the event that retesting is required, and destroyed after 1 year if not analyzed.

The list of laboratory analytes to be tested is shown in Table 5.

Table 5: List of Laboratory Analytes to be Tested

Laboratory Assessment	Analyte
Serum Chemistry	Albumin, blood urea nitrogen (BUN), creatinine, direct bilirubin, total bilirubin, aspartate aminotransferase [AST, SGOT], alanine aminotransferase [ALT, SGPT], ALP, GGT, electrolytes [calcium, chloride, potassium, sodium], glucose, total protein, and blood lipids (total cholesterol, LDL, HDL and very low density lipoprotein [VLDL] fractions and triglycerides [TG]), magnesium, phosphorus, bicarbonate, unconjugated (indirect) bilirubin, conjugated (direct) bilirubin, free fatty acids
Hematology	Hemoglobin, hematocrit, white blood count with differential, neutrophils, lymphocytes, monocytes, eosinophils, basophils, platelets, red blood cell count (including MCV, HBE [MCH], MCHC)
Coagulation	Prothrombin time (PT), partial thromboplastin time (PTT), international normalized ratio (INR)
Urinalysis	pH, specific gravity, total protein, glucose, ketones, bilirubin, blood, microscopic exam, urobilinogen, albumin, creatine, leucocytes, nitrates, albumin/creatinine ratio (if positive)
Biomarkers of Hepatic Fibrosis and/or Inflammation	IgM, C-reactive protein (CRP), TNF- α , FGF-19, CK-18, ELF, and others as determined during course of study
Measurement of Liver Fibrosis	Fibroscan
Bone Density Assessment	DEXA
Genetics	DNA including single-nucleotide polymorphisms (SNPs) that may be involved in PBC; RNA
Blood Sample for Future Analysis	PBC autoantibodies and other cytokines and interleukins TBD
Other	OCA (parent and conjugates [glyco and tauro]) and C4

The Investigator should manage subjects with clinically significant lipoprotein abnormalities using local standard of care procedures as appropriate after assessing the individual subject's total cardiovascular risk profile.

Urine-based β -hCG pregnancy tests will be performed in female subjects of childbearing potential per protocol specified visits. If a urine pregnancy test is positive, a serum pregnancy test must be performed to confirm the result. If positive, the Sponsor must be notified and the subject will be followed, as outlined in [Section 12.1.8](#) through pregnancy outcome.

MELD scores, Child-Pugh score and MRS will be calculated at quarterly (MELD scores only) and semi-annual visits based on serum chemistry and coagulation.

13. STATISTICAL METHODS

A statistical analysis plan (SAP), providing details about the specific planned analyses and hypothesis tests, will be prepared and approved by the Sponsor and its designees prior to study database lock, propensity score determination, and unblinding of the double-blind subject treatment assignments.

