13.1. Efficacy Analysis

13.1.1. Analysis Populations

The following subject populations will be evaluated and used for presentation and analysis of the data:

- The Randomized Population will include all randomized subjects.
- The Intent-to-Treat (ITT) Population will include all randomized subjects who receive any amount of investigational product (OCA or placebo). The ITT Population will be the primary population used for efficacy analyses. Treatment assignment will be based on the randomized treatment.
- The Safety Population will include all subjects who received any amount of investigational product (placebo or OCA). The Safety Population will be the primary population used for safety analyses. Treatment assignment will be based on the treatment actually received.
- The PK population will include all OCA subjects who have at least one confirmed fasted analyzable sample. Subjects must have been fasting for approximately 8 hours prior to the visit and must not have any major protocol deviations that potentially affect exposure levels. The PK population will be used for OCA PK analyses.
- The Overall Historical Control Population will include subjects from the United Kingdom (UK) -PBC Group and Global PBC Study Group databases with demonstrated comparability to randomized subjects in this clinical study (747-302) with respect to both subject characteristics and disease progression.
- The UK-PBC Historical Control Population will include subjects from the UK-PBC Group databases with demonstrated comparability to randomized subjects in this clinical study (747-302) with respect to both subject characteristics and disease progression.
- The Global PBC Historical Control Population will include subjects from the Global PBC Study Group database with demonstrated comparability to randomized subjects in this clinical study (747-302) with respect to both subject characteristics and disease progression.

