13.1.1.1. Comparability of Historical Controls

Utilization of both historical control/observational databases (UK-PBC and Global PBC Study Group), with more than 6000 subjects each, allow for a rigorous subject level meta-analysis. The historical databases include long-term follow up, detailed subject-level information such as

baseline clinical characteristics, longitudinal liver biochemistry, and long-term outcomes, and span a broad range of subject characteristics that may influence disease (disease state, age, gender, and regional differences in standard of care). Historical controls from both databases will be chosen based on the same study inclusion/exclusion criteria where possible.

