Propensity scores will be estimated using the available covariates that predict receiving the treatment. Only covariates and not outcome variables will be included in the propensity score estimation. Therefore, there is no chance of biasing results in favor of one treatment.

The covariates and factors collected in the historical databases will be specified in the SAP.

Propensity scores will be estimated first through a logistic regression model with treatment group as the dependent variable and the above covariates/factors as independent variables. Then the stratum boundaries are determined based on the propensity score values for both groups (OCA population and control [historical and randomized placebo]) combined or in the OCA population or historical control group alone. Based on recommendations in the literature, quintiles of the estimated propensity score from the combined group will be used to determine the stratum boundary cut-offs for the different strata.

Outcome events collected in the historical database are: death (liver-related and all-cause), liver transplant, hepatocellular carcinoma, and other. Other is defined as cirrhosis or decompensation such as ascites, variceal bleed, and encephalopathy.

The propensity score quintile will be then be used as the stratification factor in the stratified log rank test to compare randomized OCA-treated subjects in the ITT population and historical controls (Overall Historical Control Population: both the UK-PBC Group and Global PBC Study Group databases) on the following outcomes:

- Time to death (all-cause)
- Time to liver-related death
- Time to liver transplant
- Time to liver transplant or death (all-cause)

- Time to liver transplant or liver-related death
- Time to hepatocellular carcinoma

KM estimates of the distribution of the time-to-event will be tabulated and graphed by treatment group. The tabulation will include the KM estimate of the medians and corresponding 95% CIs if the medians can be estimated. The number and percent of subjects censored and with events will be presented. The hazard ratio and 95% CI will be determined based on a Cox regression model stratified by randomization strata to estimate the magnitude of the effect.

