Study 747-302 is a clinical outcomes study, supportive of Phase 3 Study 747-301 which was based on a surrogate biochemical endpoint, designed to confirm the clinical benefit of OCA treatment in patients with PBC. A retrospective observational database (Global PBC Study Group [Lammers 2013]) of patients with PBC allowed for a rigorous patient-level meta-analysis and provided an opportunity for a robust assessment of ALP and bilirubin as viable surrogate biochemical parameters and a comprehensive understanding of the natural history of the PBC disease process. Data from the Global PBC Study Group was also utilized to inform the design of the confirmatory outcomes study.

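### The SAP deadline does not mask registry outcomes, so the open choices in the historical-control comparison (use of entry criteria, comparability, index date, covariates) may be settled with control results in view

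*Protocol*

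**What the plan says.** All references are to the Protocol. Section 13 is quoted from Amendment 1, and the original version has the same words. The copy of Amendment 1.1 stops at Section 9.7.9.

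- **SAP timing (Section 13).** Approval must come "prior to study database lock, propensity score determination, and unblinding of the double-blind subject treatment assignments".
- **What the registries hold (13.1.1.1).** The two databases contain "baseline clinical characteristics, longitudinal liver biochemistry, and long-term outcomes".
- **Prior use (5.5.1).** "Data from the Global PBC Study Group was also utilized to inform the design of the confirmatory outcomes study". No such use is stated for UK-PBC.
- **Choice of controls (13.1.1.1 and 13.1.1).** "Historical controls from both databases will be chosen based on the same study inclusion/exclusion criteria where possible". Each historical control population must also show comparability to the randomized subjects "with respect to both subject characteristics and disease progression". No measure or threshold is given.
- **Covariates (13.1.8).** "The covariates and factors collected in the historical databases will be specified in the SAP".
- **Safeguard and the conclusion drawn from it (13.1.8).** "Only covariates and not outcome variables will be included in the propensity score estimation". The next sentence reads: "Therefore, there is no chance of biasing results in favor of one treatment".
- **Role (5.5.2.2 and 13.1.9).** The comparison supports the placebo comparison and is evaluated separately from it. If open-label enrolment is triggered, OCA against randomized placebo plus historical controls becomes the primary efficacy analysis.

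**The concern.** In the randomized comparison nobody knows either arm's results before unblinding, so an SAP signed before lock and unblinding is protected. The historical comparison differs. The OCA side is blinded until then, but the control side is an existing database with outcomes already in it. Someone who can see those outcomes can see how a choice of index date, covariate or comparability rule moves the control event rate. Several choices may be clinically defensible, and one that makes the controls look worse makes OCA look better.

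The trial is expected to last about 8 years, so the rule permits a late sign-off. At stake is the credibility of an analysis that Section 5.5.2.2 offers as an answer to possible bias in the placebo arm, for example from commercial OCA use, and that could become primary under 13.1.9.

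**Working it through.** **1. The plan's own figure.** The point rests on no stated figure and leaves the sample size alone. As a check, Schoenfeld's formula with HR 0.60, two-sided 5%, 80% power and 1:1 allocation gives 4 × (1.960 + 0.842)² / (ln 0.60)² = 120.3, so 121 events, as stated in 13.1.2.

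**2. Each SAP milestone against the registry outcomes.**

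| Milestone in Section 13 | What it protects | Does it mask registry outcomes? |
|---|---|---|
| Trial database lock | Trial data | No |
| Unblinding of trial subjects | Link between trial subject and treatment | No |
| Propensity score determination | The covariate model, before it is fitted | No |

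The third milestone is specific to this comparison, but it adds little. The model in 13.1.8 has treatment group as its dependent variable, so it cannot be fitted before the OCA subjects are identified.

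**3. What is fixed and what is open.**

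| Fixed in 13.1.8 | Still open in the text shown |
|---|---|
| Logistic propensity model | How the entry criteria apply where a registry lacks a field |
| Quintiles of the score from the combined group | How comparability is judged, including disease progression |
| Both registries pooled, each alone as a sensitivity analysis | Index date for registry patients |
| Stratified log rank test on six named outcomes | Propensity covariates |

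The progression criterion needs most attention. If progression is judged after the index date, selecting controls on it uses information close to the outcome, even though no outcome enters the propensity model.

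**4. Does the safeguard support the conclusion?** The protocol restricts the inputs of the propensity model. It does not restrict what is known to those who choose the controls and covariates. The statement that bias is impossible does not follow.

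**5. Size, as an illustration.** The assumptions are not in the documents:

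- True HR is 1, and the controls are registry only.
- The registry is so large that SE(log HR) ≈ 1/√d, where d is the number of OCA events.
- d is 20 to 50. For scale, the design's own assumptions give 175 × 0.305 ≈ 53 OCA events on the full composite. The 13.1.8 outcomes are narrower.
- Choices made with outcomes in view raise the control hazard by s = 5%, 10% or 15%.

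One-sided error = Φ(−1.96 + ln(1 + s) × √d), with ln(1.05) = 0.0488, ln(1.10) = 0.0953 and ln(1.15) = 0.1398.

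| OCA events | 5% | 10% | 15% |
|---|---|---|---|
| 20 | 4.1% | 6.3% | 9.1% |
| 30 | 4.5% | 7.5% | 11.6% |
| 50 | 5.3% | 9.9% | 16.6% |

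The nominal value is 2.5%. For d = 50 and s = 10%: Φ(−1.96 + 0.0953 × 7.071) = Φ(−1.286) = 9.9%.

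**6. How such a shift could arise.** Suppose the least favourable of five candidate control sets is taken, and their log hazards differ with SD 0.10 (again an assumption). Simulation gives an average HR of 0.89 when the truth is 1, a control shift of about 12% (1/0.89). False OCA wins are then 8.3% at 20 events and 15.8% at 53. With no choice among sets the figures are 3.7% and 5.6%, so part of the excess is variation between sets and not selection.

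**The case against.** The strongest reply is that this is an omission rather than an error. Section 13 sets a latest date, nothing prevents earlier approval, and a firewall around a registry extract often sits in the SAP or a data-access plan, neither of which is at hand. That limits the point to what the rule permits. It does not remove it: the protocol fixes the deadline itself, and it asserts that bias is excluded on grounds that do not support the assertion.

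Other objections stand and narrow the point:

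- **Much is already fixed.** A reader might infer that the whole historical analysis, strata included, can be tuned late. The right-hand column of the second table marks the limit.
- **Access is not shown.** A reader might infer that the SAP authors have seen the outcomes or have chosen controls by them. The documents say only that Global PBC data informed the design. They do not say who holds the outcomes. Section 7.1 calls some controls concurrent, so some outcomes may not yet exist at sign-off.
- **The role is limited.** A reader might infer that the trial's type I error is inflated. By default this comparison lies outside the testing hierarchy in 13.1.11. It becomes primary only if, after 4 years of accrual, at least 2 more years are needed (total at least 10 years), and 13.1.2.1 requires a change of allocation to be documented in a protocol amendment.
- **Dilution.** Under 13.1.9 randomized placebo is also among the controls, so a registry-only shift counts for less than the table shows.
- **Version.** Amendment 1.1 lists the same Section 13 headings, but carry-over of the text cannot be confirmed.

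**Conclusion.** The point holds in limited form. The SAP deadline leaves registry outcomes unmasked while entry-criteria application, comparability, index date and covariates are still open, and the no-bias statement in 13.1.8 is unsupported. The documents show that selection with control results in view is possible. They do not show that it happened.

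The approximate error rates of 4-5%, 6-10% and 9-17% are illustrations. They depend on the assumed hazard shifts, 20 to 50 OCA events, a large registry and registry-only controls. The randomized primary analysis and its 121 events are unaffected. The weight is moderate while the comparison is supportive and would rise if 13.1.9 were triggered.

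**What to change.** In Section 13 and its subsections:

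1. State that control eligibility, the comparability criteria, index date and propensity covariates are approved, and the control set locked, on a registry extract without outcome fields, or by a team masked to them. Outcomes are released afterwards, with the dates documented.
2. Lock the propensity scores before outcomes are linked. The model needs the treatment codes, so this step comes after the control set is locked.
3. In 13.1.1, base comparability on baseline characteristics or pre-index course, not on progression after the index date.
4. In 13.1.8, delete the sentence that says bias is impossible.

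Before editing, check whether Section 13 of Amendment 1.1 already differs. The cost is a two-stage registry extract and earlier sign-off of one SAP section. No patients, visits or procedures are added, and the randomized analysis does not change.

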13.1. Efficacy Analysis

13.1.1. Analysis Populations

The following subject populations will be evaluated and used for presentation and analysis of the data:

- The Randomized Population will include all randomized subjects.
- The Intent-to-Treat (ITT) Population will include all randomized subjects who receive any amount of investigational product (OCA or placebo). The ITT Population will be the primary population used for efficacy analyses. Treatment assignment will be based on the randomized treatment.
- The Safety Population will include all subjects who received any amount of investigational product (placebo or OCA). The Safety Population will be the primary population used for safety analyses. Treatment assignment will be based on the treatment actually received.
- The PK population will include all OCA subjects who have at least one confirmed fasted analyzable sample. Subjects must have been fasting for approximately 8 hours prior to the visit and must not have any major protocol deviations that potentially affect exposure levels. The PK population will be used for OCA PK analyses.
- The Overall Historical Control Population will include subjects from the United Kingdom (UK) -PBC Group and Global PBC Study Group databases with demonstrated comparability to randomized subjects in this clinical study (747-302) with respect to both subject characteristics and disease progression.
- The UK-PBC Historical Control Population will include subjects from the UK-PBC Group databases with demonstrated comparability to randomized subjects in this clinical study (747-302) with respect to both subject characteristics and disease progression.
- The Global PBC Historical Control Population will include subjects from the Global PBC Study Group database with demonstrated comparability to randomized subjects in this clinical study (747-302) with respect to both subject characteristics and disease progression.

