9. TREATMENT OF SUBJECTS

9.1. Investigational Product Treatment Regimen

The term investigational product refers to either OCA (provided as part of this clinical study) or placebo.

Two treatment groups will be evaluated: placebo and OCA. Investigational product will be administered orally, once daily for the duration of the study. Each dose will be made up of 1 tablet (ie, one 5 mg OCA tablet or one 10 mg OCA tablet, or matching placebo).

Investigational product will be taken orally, once daily. Subjects will be instructed to begin dosing on the day after the Day 0 visit (ie, on Day 1) and to take investigational product at approximately the same time each day. Subjects must be instructed to swallow the tablet whole; they must not chew, divide, or crush the tablet.

9.1.1. Dose Adjustment Beginning at Month 3

After 3 months of treatment with investigational product, the dose of investigational product should be increased in a blinded manner and based on tolerability; this may occur at the Month 3 visit, or at any study visit thereafter. Titration above 10 mg OCA is not permitted.

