13.1.2.1. Sample Size Re-Estimation Plan

Conducting a long-term outcomes study given the low disease prevalence, relatively slow disease progression, and ethical considerations, which in combination will impact recruitment and event rates, is inherently difficult. As stated in ICH E9, in long-term trials there is an opportunity to check the assumptions that underlay the original design and sample size calculations. The power stated above depends on the total number of events. Thus, the overall survival function can be estimated without unblinding.

Therefore, starting approximately 2 years after the first subject is randomized, the aggregate event rate and sample size based on recruitment and retention will be evaluated in a blinded manner quarterly. This evaluation will determine if any increases in number of subjects are required in order to obtain a total of 121 adjudicated events for the final analysis in the combined groups. Specifically, the pooled number of events will be available during the study in a blinded manner, without any knowledge of the comparative efficacy in the treatment groups. This method for evaluating the sample size does not inflate the type I error rate. Additional subjects may be enrolled as appropriate.

If after 4 years of accruing subjects, despite increases in the number of subjects, it is determined that at least an additional 2 years (ie, total study duration of at least 10 years) are needed to randomize sufficient subjects to achieve a total of 121 adjudicated events, all subjects enrolled from that point forward will receive open-label OCA. Previously randomized subjects will continue to be treated in a blinded manner with either OCA or matching placebo. If this

modification is implemented, the alternative primary efficacy analysis is specified in [Section 13.1.9](#).

Any revised sample size or changes to treatment allocation will be justified and documented in a protocol amendment and in the CSR.

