13.2. Safety Analysis

Safety data, including AEs and clinical laboratory observations, will be summarized by treatment group using the Safety Population.

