13.2.1. Adverse Events

AEs will be coded using the Medical Dictionary of Regulatory Activities. Summary tables of treatment-emergent AEs will be provided. The incidence of TEAEs will be tabulated by system organ class and preferred term for each treatment group, and by severity and relationship to treatment. Tables of TEAEs leading to investigational product discontinuation and SAEs will be provided.

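### If the open-label switch is used, the Safety Population as defined puts later-entering, unblinded OCA subjects in the OCA column and none in placebo, so crude adverse-event incidence compares groups with unequal follow-up

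*Protocol*

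**What the plan says.** Protocol Section 13.1.1 defines the primary set for safety as follows: "The Safety Population will include all subjects who received any amount of investigational product (placebo or OCA"). It adds: "Treatment assignment will be based on the treatment actually received". The Intent-to-Treat Population in the same list is narrower: "all randomized subjects who receive any amount of investigational product (OCA or placebo").

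Section 9.1 settles what counts as investigational product: "The term investigational product refers to either OCA (provided as part of this clinical study) or placebo". That wording is not limited to blinded supply. The same section states: "Two treatment groups will be evaluated: placebo and OCA". The Section 9.1 text is the same in Amendments 1 and 1.1.

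Section 13.1.2.1 provides for a switch. If, after 4 years of accrual and despite sample-size increases, at least 2 further years are needed, then "all subjects enrolled from that point forward will receive open-label OCA", while subjects already randomized stay on blinded OCA or placebo. Total duration would then be at least 10 years.

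On reporting, Section 13.2 states: "Safety data, including AEs and clinical laboratory observations, will be summarized by treatment group using the Safety Population". Section 13.2.1 states: "The incidence of TEAEs will be tabulated by system organ class and preferred term for each treatment group". Section 12.1.4.1 collects adverse events from consent until participation ends. The Amendment 1.1 synopsis keeps the OCA-placebo safety comparison in the Safety Population.

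The Section 13 wording is from Amendment 1; the original protocol reads the same on these points. The document breaks off in Section 9.7.9 of Amendment 1.1, so its Section 13 cannot be checked.

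**The concern.** Taken together, these rules change the safety table once the switch is made. Open-label subjects received study OCA, so they are in the Safety Population. They are classified by what they received, and the only group available to them is OCA. They enter after the last randomized subject, so their possible follow-up is shorter, and they and their investigators know the treatment. The placebo column receives no such subjects.

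Because events are collected throughout participation, crude incidence rises with time on study. Mixing shorter-followed subjects into one column lowers its incidence for any event that builds up over years. A modest excess on OCA could be diluted or hidden in the planned table. Comparing OCA with placebo for safety and tolerability is a stated secondary objective (Section 6.2), so this table matters.

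**Working it through.** **The plan's own figure.** The protocol gives no adverse-event rate to reproduce. Its 121 events do reproduce: 4 × (1.960 + 0.842)² / (ln 0.60)² = 120.3, rounded up to 121, with power 80.2%. That figure does not bear on this point.

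**Inputs from the protocol.** 350 planned subjects allocated 1:1, so 175 per arm; switch possible after 4 years of accrual; total duration at least 10 years.

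**Assumptions not in the protocol.** Uniform randomized entry over years 0-4; uniform open-label entry over years 4-6; cut-off at exactly year 10; 100 or 175 open-label subjects; constant event hazard h, equal in all groups; no dropout.

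**Follow-up.** Randomized subjects have 6 to 10 years (mean 8). Open-label subjects have 4 to 6 years (mean 5). The mean is shorter by (8 − 5)/8 = 37.5%.

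**Formula.** With follow-up uniform on (a, b), the expected crude incidence is P = 1 − [exp(−ha) − exp(−hb)] / [h(b − a)].

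**At h = 0.05 per year**
- Randomized, either arm: 1 − (0.7408 − 0.6065)/0.20 = 32.9%.
- Open-label: 1 − (0.8187 − 0.7408)/0.10 = 22.1%.
- OCA column, 175 + 100: (175 × 32.9 + 100 × 22.1)/275 = 28.9%.
- OCA:placebo ratio: 28.9/32.9 = 0.88. The true ratio is 1.00.

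| Hazard per year | Placebo | Open-label OCA | Pooled OCA, 100 open-label | Ratio | Pooled OCA, 175 open-label | Ratio |
|---|---|---|---|---|---|---|
| 0.05 | 32.9% | 22.1% | 28.9% | 0.88 | 27.5% | 0.84 |
| 0.02 | 14.8% | 9.5% | 12.9% | 0.87 | 12.1% | 0.82 |

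**Sensitivity**
- With 175 per arm, 50 to 175 open-label subjects, open-label follow-up of 4-6, 2-6 or 0-6 years, and hazards of 0.02 to 0.20 per year, the ratio runs from 0.70 to 0.95. It is below 1 throughout. With 100 randomized per arm and 175 open-label, it falls as low as 0.61.
- Masking: let OCA truly raise the hazard 1.25-fold over a placebo hazard of 0.05. Randomized subjects show 39.2% against 32.9%, a ratio of 1.19. Pooling 175 open-label subjects followed 4-6 years gives 33.0%, a ratio of 1.00.
- Early events: at a hazard of 2 per year, the ratio is 1.00 with 4-6 years of open-label follow-up, and about 0.95 or higher if open-label follow-up runs from 0 to 6 years.
- Open-label reporting: to cancel the dilution, it would have to raise the open-label hazard about 1.6-fold (follow-up 4-6 years), or 2.7- to 4.0-fold (follow-up 0-6 years).

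**The case against.** **The pooled column is inferred.** No sentence says that open-label subjects share a column with randomized OCA. Elsewhere, in the synopsis and Section 9.4, treatment groups are the allocated arms, and Section 13.1.9 pools in explicit terms, for efficacy only. This is a fair reading of the phrase, but it does not displace the rule that takes all dosed subjects by treatment received. With two groups defined, an open-label subject in the Safety Population has only the OCA column to go to.

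**The switch needs an amendment, and an SAP may follow.** Section 13.1.2.1 requires an amendment for changes in sample size or allocation, and that amendment could define a separate safety display. This stands as a mitigating point. Still, the protocol already prespecifies the efficacy consequence of the switch in Section 13.1.9 and leaves the safety definition as it is. The point therefore concerns a rule that is stated, not detail left to the SAP. The absence of exposure adjustment alone would not be a finding.

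**Three stronger readings go too far.**
- A reader might infer that every event would look rarer on OCA. Section 5.5.2.1 reports that pruritus typically appeared within a month, so its crude incidence hardly depends on follow-up, and unblinded reporting could raise it.
- A reader might infer that open-label subjects all start at least 4 years after randomized ones. That holds only against the first randomized subject, since randomization may continue up to the switch. In the model above, the mean gap is 3 years.
- A reader might infer that the randomized safety comparison is lost. It is displaced from the primary table, but the data remain and Section 13.1.1 also defines a Randomized Population. The major hepatic outcomes are also analysed as time to event in randomized OCA against randomized placebo (Section 13.1.5), and nothing withdraws that if the switch occurs.

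**Conclusion.** The point holds, conditionally. If the open-label switch is used and Section 13.1.1 is followed as written, the OCA and placebo columns of the safety tables differ in follow-up and blinding. Crude incidence of events that accrue over time is then understated on OCA relative to placebo. Follow-up has little effect on early-onset events, and open-label reporting may push in the opposite direction.

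The size is illustrative: a ratio of 0.82 to 0.88 under no true difference in the four tabulated cases, and 0.70 to 0.95 across the wider range with 175 randomized per arm. These figures are not the plan's own timings. The open-label entry window, exact cut-off, cohort size, hazards and absence of dropout are all assumed. The arm size follows the original plan, although the switch presupposes that numbers were increased first. If the switch is never used, the problem does not arise. The conclusion also assumes that the unseen Section 13 of Amendment 1.1 keeps the Amendment 1 wording.

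**What to change.** In Sections 13.1.1 and 13.2, state that the OCA-placebo safety comparison uses randomized, dosed subjects only, classified by treatment received. Show any open-label OCA cohort in a separate column that is not pooled for comparison with placebo. Where a pooled OCA summary is wanted, give subjects with events per 100 person-years alongside the counts and percentages.

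Under equal true hazards and the assumptions above, the comparison in randomized subjects returns a ratio of 1.00. The cost is a sentence in each section and one extra table column, with no new data. The drawback is a smaller OCA column in the comparison with placebo. Making the change before any switch keeps the choice independent of emerging safety results.
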